2. STUDY OBJECTIVES

2.1. Primary Objective

The primary objective of the study is:

- to evaluate the PK of a single dose of AMG 890 in Chinese subjects with elevated serum lipoprotein(a) (Lp(a)).

2.2 Secondary Objective

The secondary objectives of the study are:

- to evaluate the safety and tolerability of a single dose of AMG 890 in Chinese subjects with elevated serum Lp(a).
- to evaluate the pharmacodynamic of a single dose of AMG 890 in Chinese subjects with elevated serum Lp(a).

3. STUDY ENDPOINTS

3.1. Primary Endpoints

The primary endpoints are:

- maximum serum concentration (C_{max});
- area under the serum concentration-time curve (AUC);
- Additional PK parameters may include, but are not limited to: time to maximum observed concentration (t_{max}), half-life ($t_{1/2}$), apparent volume of distribution during the terminal elimination phase (V_z/F), and apparent total body clearance (CL/F).

3.2. Secondary Endpoints

The secondary endpoints are:

- Treatment-emergent adverse events;
- clinical laboratory tests;
- 12-lead electrocardiograms (ECGs);
- vital signs;
- lipids;
- serum Lp(a).

4. STUDY DESIGN

This study is an open-label, randomized, single-dose, parallel-group study in Chinese subjects with elevated serum Lp(a) to assess the PK, safety and tolerability, and PD of AMG 890.

Subjects will be randomized in a 1:1 ratio to receive a single SC dose of AMG 890 at █ mg (Group A) or █ mg (Group B). A total of approximately 24 subjects (12 per group) will be enrolled in this study.

Subjects must be living in mainland China, Hong Kong, or Taiwan, and be of Chinese ancestry with an age of 18 to 60 years old, and have body mass index (BMI) of 18 to 32 kg/m² and serum Lp(a) \geq 70 nmol/L (or approximately \geq 27 mg/dL).

Subjects will be assigned to 1 of 2 treatment groups shown in [Table 1](#).

[figure not shown]
Table 1: Treatment Groups

Group	Number of subjects	Dose
-------	--------------------	------

A	12	█ mg SC
B	12	█ mg SC

An overview of the study design is shown in Figure 1 below.

Figure 1: Study Schematic

Potential subjects will be screened to assess their eligibility to enter the study within 28 days prior to the first dose administration. Subjects will be admitted into the clinic on Day -1 and be confined to the clinic until discharge on Day 4. Subjects will return to the clinic for outpatient visits on Days 7, 15, 29, 57, 85, 113, 155, and 183, and at the End of Study (EOS) visit on Day 225. A telephone visit will be scheduled for TEAE assessments on Day 211. The total duration of study participation for each subject (from Screening through EOS visit) is anticipated to be approximately 253 days (36 weeks).

The start of the study is defined as the date the first subject signs an Informed Consent Form (ICF). The point of enrollment occurs at the time of subject randomization number allocation. The enrollment date is the same as the randomization date. The EOS for overall study is defined as the date of the last subject's last assessment (scheduled or unscheduled).

5. SAMPLE SIZE JUSTIFICATION

Approximately 24 subjects (12 per group) will be enrolled in the study. No formal statistical hypothesis testing will be performed. The sample size of 12 subjects per group is based on studies of similar nature and was not based on power calculations. Considering a 33.3% drop-out rate, 8 subjects per cohort provides an approximately 90% confidence of observing a case of a TEAE in each cohort at an incidence of 25%.

6. STUDY TREATMENTS

The study treatment names and ordering to be used in the TFLs are presented in Table 2 below.

Table 2: Presentation of Study Treatments in TFLs

Study Treatment	Treatment Abbreviation	Order in TFLs
Group A: [REDACTED] mg administered as a single 1 mL ([REDACTED] mg/mL) SC injection	[REDACTED] mg AMG 890	1
Group B: [REDACTED] mg administered as three 1.0 mL ([REDACTED] mg/mL) SC injections	[REDACTED] mg AMG 890	2

All treatments described above are the planned treatments. Subject disposition and baseline will be summarized by randomized treatment group, PK and safety analysis will be summarized by actual treatment received., and dose levels will be displayed in increasing order.

7. DEFINITIONS OF ANALYSIS SETS

Any protocol deviations will be considered prior to database lock for their importance and taken into consideration when assigning subjects to analysis sets.

7.1. All Subjects Analysis Set

The all subjects analysis set will include all randomized subjects.

7.2. Safety Analysis Set

The safety analysis set will include all randomized subjects who received AMG 890.

7.3. Pharmacokinetic Analysis Set

The PK analysis set will include all randomized subjects who received AMG 890 and have evaluable PK data.

7.4. Pharmacodynamic Analysis Set

The PD analysis set will include all randomized subjects who received AMG 890 and have evaluable PD data.

8. STATISTICAL METHODOLOGY

8.1. General

Listings will be provided for all data captured in the database, with the exception of medical history. Listings will include all subjects in the all subjects analysis set and include data up to the point of study completion or discontinuation. Any subject who discontinued the study will be listed in the applicable listing. Summaries and statistical analyses will include the subjects assigned to the relevant analysis sets based on data type.

Data analysis will be performed using the SAS® statistical software package Version 9.4 or higher.

Analysis Data Model (ADaM) datasets will be prepared using Clinical Data Interchange Standards Consortium (CDISC) ADaM Version 2.1 (or higher if upversioned during the study) and CDISC ADaM Implementation Guide Version 1.1. Pinnacle 21 Community Validator Version 4.2.1 will be utilized to ensure compliance with CDISC standards.

Caution should be used when interpreting results from the statistical analyses conducted in this study because the sample size is not based on power calculations.

Where reference is made to 'all calculations', this includes, but is not limited to, summary statistics, statistical analyses and any parameter derivations.

8.1.1. Calculation of the Summary Statistics

For continuous data the following rules will be applied:

- Missing values will not be imputed, unless specifically stated otherwise.
- Unrounded data will be used in the calculation of summary statistics.
- If number of subjects with valid observations (n) <3, summary statistics will not be calculated, with the exception of n, minimum, and maximum.
- As Early Termination data is not associated with any scheduled timepoint, it will be excluded from all calculations of summary statistics.

For categorical data the following rules will be applied:

- If the categories of a parameter are ordered (eg, adverse event [AE] severity), all categories between the possible minimum and maximum categories will be included, even if n = 0 for a given category. If the categories are not ordered (eg, race), only those categories for which there is at least 1 subject represented will be included.
- Missing values will not be imputed, or unless specifically stated otherwise. A 'missing' category will be included for any parameter for which information is missing. This will ensure that the population size totals are consistent across different parameters.

8.1.2. Repeat and Unscheduled Readings

For vital signs and ECG data only, any predose value recorded in addition to the original value or a postdose value recorded within 15 minutes of the original value will be defined as a repeat value; any postdose value recorded more than 15 minutes after the original value will be defined as an unscheduled value. For all other data types (eg, laboratory parameters), any value recorded in addition to the original value will be defined as an unscheduled value.

The original value will be replaced by the last associated repeat value in all calculations.

As unscheduled values are not associated with any scheduled timepoint, they will be excluded from all calculations.

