Resting 12-lead ECGs will be recorded after the subject has been supine and at rest for at least 5 minutes at the times indicated in the Schedule of Assessments in [Appendix 9](#). If the subject is unable to be in the supine position, the subject should be in the most suitable recumbent position possible. The ECG must include the following measurements: heart rate, QRS, QT, QTc, and PR intervals. The ECG will be single trace (1 x 10-second tracing), prior to safety blood draws or invasive procedures.

Single 12-lead ECGs will be repeated twice (within a total of five minutes from the start of the first to the completion of the third), and an average taken of the 3 readings, if either of the following criteria apply:

- QTcF is > 500 ms
- QTcF change from the baseline (predose) is > 60 ms.

The Investigator (or designee [e.g., designated site physician]) will review all ECGs. Once signed, the original ECG tracing will be retained with the subject's source documents. At the request of the sponsor, a copy of the original ECG will be made available to Amgen. Additional 12lead ECGs may be performed at other times if judged to be clinically appropriate or if the ongoing review of the data suggests a more detailed assessment of ECGs is required. The investigator (or designee) will perform a clinical assessment of each 12-lead ECG.

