1. INTRODUCTION

This SAP has been developed in alignment with the clinical study protocol (dated 07 Oct 2020).

This SAP describes the planned analysis of the pharmacokinetic (PK), pharmacodynamic (PD) and safety and tolerability data from this study. A detailed description of the planned TFLs to be presented in the clinical study report (CSR) is provided in the accompanying TFL shells document.

In general, the analyses are based on information from the protocol, unless they have been modified by agreement with Amgen Inc. A limited amount of information about this study (eg, objectives, study design) is given to help the reader's interpretation. This SAP must be finalized prior to the lock of the clinical database for this study. When the SAP and TFL shells are approved, they will serve as the template for this study's CSR.

Significant changes from the protocol-specified analyses are described in section 10 of this SAP. If post-hoc analyses are required to supplement the planned analyses described in this SAP, they may be performed and will be identified accordingly in the CSR. Any substantial deviations from this SAP will be agreed with Amgen Inc. and identified in the CSR.

This SAP is written with consideration of the recommendations outlined in the International Conference on Harmonisation (ICH) E9 guideline *Statistical Principles for Clinical Trials* and ICH E3 guideline *Structure and Content of Clinical Study Reports*.^{1,2}

The document history is presented in [Appendix 1](#).

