8.6.3. Vital Signs Parameters

All vital signs parameters will be listed; any value outside the clinical reference range will be flagged.

Summary tables along with change from baseline and percent change from baseline will be provided for all vital signs parameters based on safety analysis set. The baseline is defined as the last reading before dosing.

8.6.4. 12-lead Electrocardiogram Parameters

All 12-lead ECG parameters will be listed; any value outside the clinical reference range will be flagged.

Summary tables by timepoint along with change from baseline and percent change from baseline will be provided for all 12-lead ECG parameters based on safety analysis set. The baseline is defined as the last reading before dosing.

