10. SIGNIFICANT CHANGES FROM THE PROTOCOL-SPECIFIED ANALYSES

There were no significant changes from the protocol-specified analyses.

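### Should the SAP analyse the mean of three ECG readings after a QTcF trigger, as Protocol 7.6.3 describes, instead of the last repeat?

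*SAP*

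**What the plan says.** Protocol 7.6.3 calls for a single 10-second tracing at each scheduled time. If the QTcF trigger is met, it continues: "Single 12-lead ECGs will be repeated twice (within a total of five minutes" from the start of the first to the end of the third, "and an average taken of the 3 readings, if either of the following criteria apply". The criteria are QTcF above 500 ms and a change from predose above 60 ms.

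SAP 8.1.2 covers vital signs and ECGs together. After dosing, "a postdose value recorded within 15 minutes of the original value will be defined as a repeat value", and "The original value will be replaced by the last associated repeat value in all calculations". SAP 8.1 gives that last phrase a wide scope: "this includes, but is not limited to, summary statistics, statistical analyses and any parameter derivations". The ECG section, 8.6.4, has no averaging step and no exception: "Summary tables by timepoint along with change from baseline and percent change from baseline will be provided for all 12-lead ECG parameters". It takes the last predose reading as baseline.

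On departures from the protocol, SAP section 1 states: "Significant changes from the protocol-specified analyses are described in section 10 of this SAP". Section 10 then reads: "There were no significant changes from the protocol-specified analyses".

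**The concern.** The protocol's five-minute set lies wholly inside the SAP's 15-minute window, so every triggered postdose set falls under the last-repeat rule. Both rules cannot supply the analysis value for the same three tracings. The last-repeat rule suits vital signs, where Protocol 7.6.4 asks for one repeat and no averaging. It looks as if it was carried over to ECGs without regard to 7.6.3.

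ECGs are a named secondary endpoint, and a reader looking for a QT signal goes first to triggered timepoints. Two analysts, one following each document, would report different values there. The visit maximum could differ, and the visit mean slightly. Because section 10 lists nothing, a reader cannot tell whether the average was set aside on purpose.

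**Working it through.** **The plan's own figures.** Neither document gives a number on this point. The only design figure is the chance of seeing at least one TEAE at 25% incidence with 8 subjects: 1 − 0.75^8 = 0.8999, which matches the stated 90%. The 8 is 12 × (1 − 1/3). It is used below as the smaller group size.

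**Illustration (invented readings).** For 505, 490 and 481 ms the mean is 1476/3 = 492 ms and the last reading is 481 ms. The gap is 11 ms for that subject and 11/12 = 0.9 ms on a 12-subject visit mean. This is an example, not a bound.

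**Model inputs.**
- From the documents: trigger at a change above 60 ms, and 7 postdose ECGs × 24 subjects = 168 (counted from Protocol Appendix 9).
- Assumed: SD of true change sT = 10, 15 or 20 ms, and single-trace error SD sE = 6, 8 or 10 ms, with the same error in the single predose tracing. Only upward changes count, and the 500 ms criterion is left out.

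**Formulas.** True change T ~ N(μ, sT). Errors e1, e2, e3 (postdose) and eb (predose) are independent N(0, sE). The trigger is T + e1 − eb > 60.
- S = √(sT² + 2sE²), a = (60 − μ)/S, P = 1 − Φ(a), λ = φ(a)/P.
- Expected triggers = 168 × P.
- Mean of three minus last = (e1 + e2 − 2e3)/3. Given a trigger, its mean is (sE²/S)λ/3 and its variance is [v1 + 5sE²]/9, with v1 = sE² − (sE²/S)²λ(λ − a).
- The mean absolute difference comes from the folded normal.
- Errors against the true change: last = e3 − eb; mean of three = (e1 + e2 + e3)/3 − eb.

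**One setting in full (sT = 20, sE = 10, μ = 0).** S = √600 = 24.49, a = 2.449, P = 0.00715, so 168 × P = 1.20. λ = 2.777. The mean difference is (100/24.49) × 2.777/3 = 3.78 ms. v1 = 100 − 16.67 × 2.777 × 0.328 = 84.8, so the SD is √(584.8/9) = 8.06 ms.

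**All nine settings, no QT effect (ms):**

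| sT | sE | Expected triggers | Mean of three minus last | SD | Mean absolute difference | RMSE last | RMSE mean of three |
|---|---|---|---|---|---|---|---|
| 10 | 6 | 0.0004 | 4.37 | 4.82 | 5.32 | 15.38 | 18.46 |
| 10 | 8 | 0.006 | 5.93 | 6.38 | 7.15 | 20.68 | 24.87 |
| 10 | 10 | 0.04 | 7.15 | 7.95 | 8.75 | 25.09 | 29.94 |
| 15 | 6 | 0.04 | 2.60 | 4.85 | 4.41 | 11.35 | 12.20 |
| 15 | 8 | 0.12 | 3.93 | 6.44 | 6.07 | 16.01 | 17.71 |
| 15 | 10 | 0.30 | 5.17 | 8.02 | 7.68 | 20.47 | 22.87 |
| 20 | 6 | 0.48 | 1.69 | 4.87 | 4.12 | 9.76 | 9.45 |
| 20 | 8 | 0.76 | 2.71 | 6.47 | 5.61 | 13.68 | 13.81 |
| 20 | 10 | 1.20 | 3.78 | 8.06 | 7.13 | 17.70 | 18.30 |

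**Visit mean, one triggered subject.** 4.12/12 = 0.34 to 8.75/12 = 0.73 ms with 12 subjects; 4.12/8 = 0.51 to 8.75/8 = 1.09 ms with 8.

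**Accuracy.** With no effect the mean of three has lower RMSE only at sT = 20, sE = 6. Elsewhere it is up to 20% higher, because it keeps the reading that was selected for being high. At mean effects of 20 and 40 ms it is lower in 4 and 9 of 9 settings, by at most 15%. Overall that is 1 + 4 + 9 = 14 of 27.

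**The case for a change.** The strongest case for a change is consistency. Nothing in Protocol 7.6.3 confines the average to clinical review. The protocol's analysis text names no other ECG value, and an average that no analysis uses invites a question. The remedy would cost one sentence. The rules can also disagree on whether a triggered set exceeds 500 ms. Simulating a trigger on a first reading above 500 ms, with true QTcF of 485 to 495 ms and single-trace SD of 5 to 12 ms (all assumed), they disagree in about 0.1% to 27% of triggered sets.

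What stands is that the texts differ and the SAP does not say how they relate. The rest is weaker.
- The averaging sentence is in an assessment section, next to investigator review and the signing of tracings. Protocol section 8 asks only for descriptive ECG summaries and leaves further detail to the SAP. Section 10 covers significant changes from protocol-specified analyses, so its silence is not shown to be a breach.
- The SAP text plans no count of subjects above 500 ms, so the disagreement on that threshold reaches no analysis it describes.
- The site might enter the average as the final ECG record. Neither document says so, and the CRF is not supplied, so nothing rests on this.
- A simple switch to the mean raises its own questions. A predose set would be averaged while 8.6.4 still takes the last predose reading as baseline, and a set with fewer than three readings would have no rule.

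**Conclusion.** The mismatch in wording is real, but it does not call for a change. SAP 8.1.2, read with 8.1, gives the analyst one value for a triggered timepoint, fixed in advance. Choosing between the mean and the last reading is a fair trade-off: the mean averages out noise but keeps the selected trigger reading. Without a QT effect it has the higher error in 8 of 9 settings; at a 40 ms effect it has the lower error in all 9.

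The stakes are small. Expected triggers are below 1 in 8 of the 9 no-effect settings, and one triggered subject moves a visit mean by 0.3 to 1.1 ms. A visit maximum changes only if that subject holds it. The safety summaries are descriptive, and SAP 8.1 and 8.6.4 list the ECG data, so the readings entered in the database remain visible. Protocol 4.2 also excludes QTcF above 450 ms in men and 470 ms in women at Screening, which makes the 500 ms trigger less likely.

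These sizes rest on assumed SDs, normal errors and no QT effect. With a large effect, triggers would no longer be rare and averaging would gain some accuracy. Even then the study makes no inference from ECGs, and declaring the difference in section 10 would change no reported number.

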7.1 Study Procedures

7.1.1 Screening, Enrollment, and/or Randomization

Informed consent must be obtained before completing any screening procedure or discontinuation of standard therapy for any disallowed therapy. After the subject has signed the ICF, the site will screen the subject to assess eligibility for participation. The screening window is up to 40 days.

All screening evaluations must be completed and reviewed to confirm that potential subjects meet all eligibility criteria. The investigator will maintain a screening log to record details of all subjects screened and to confirm eligibility or record reasons for screening failure, see Section 4.3 as applicable.

If a subject has not met all eligibility criteria at the end of the screening period, the subject will be registered as a screen failure. Screen failed subjects may be eligible for re-screening 3 times.

Once the subject is registered as rescreened, a new 40-day screening window will begin. Subjects will retain the same unique identification number assigned at the original screening. If the rescreening period begins more than 40 days after the original signing of the ICF, all screening procedures, including informed consent, must be repeated as well.

Laboratory assessments used to determine subject eligibility may be repeated once for confirmation, allowing for up to a total of two assessments during the 40-day screening period, if necessary, before the subject is considered a screen failure. If any assessments are repeated

during the screening period, the value that is closest to the enrollment date will apply for the determination of eligibility.

If the initial BP measurement is elevated, the assessment may be repeated again at least 15 minutes later and the lower of the 2 readings may be used for Screening.

Subjects will be assigned a randomization number based in sequential order in which they qualified to be randomized, in accordance with the randomization schedule. Subjects are considered randomized once a unique subject randomization number has been assigned.

The point of enrollment occurs at the time of subject randomization number allocation. The enrollment date is the same as the randomization date.

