Appendix 9. Schedule of Assessments

Table 5. Schedule of Assessments

PROCEDURE	Screening	Check-in	Treatment Period										
	Study Day	-40 to -2	-1	1	2	3	6	9	12	24	36	48	72
Study Time (Hours)			Predose	0	1	2	3	6	9	12	24	36	48
Study Time (Minutes)				0	30	60	120	180	360	540	720		
GENERAL AND SAFETY ASSESSMENTS													
Informed Consent	X												
In-house Residency ^a													
Physical Examination ^b	X	X											X
Medical History	X	X ^c											
Weight	X	X											
Height	X												
ECG ^d	X		X					X			X		
Vital Signs ^e	X	X	X			X	X			X	X	X	X
TEAEs ^f					◀								▶
Serious TEAEs ^f													
Concomitant Therapy Review ^g													
LABORATORY ASSESSMENTS													
Pregnancy Test ^h	X	X											
Coagulation Panel	X	X									X		X
Chemistry & Hematology ^{i, o}	X	X									X		X
Serology	X												
Urinary Drug Screen	X	X											
Alcohol Urine Test	X	X											
Urinalysis	X	X											X
eGFR ^j	X												
FSH ^k	X												
Anti-Olpasiran Antibody				X									
PHARMACOKINETIC ASSESSMENTS													
Olpasiran Serum PK Collection ^l				X	X	X	X	X	X	X	X	X	X
PHARMACODYNAMIC ASSESSMENTS													
Lp(a) ^m	X		X								X		X
Lipid Panel ^{n, o}	X		X										

PROCEDURE	Screening	Check-in	Treatment Period									
			1					2				
Study Day	-40 to -2	-1										
Study Time (Hours)			Predose	0	1	2	3	6	9	12	24	36
Study Time (Minutes)				0	30	60	120	180	360	540	720	
STUDY TREATMENT												
Olpasiran administration							X					

Abbreviations: Apo A1 = apolipoprotein A1; Apo B = apolipoprotein B; ECG = electrocardiogram; eGFR = Estimated glomerular filtration rate; FSH = follicle-stimulating hormone; HDL-C = High-density lipoprotein; LDL-C = low-density lipoprotein; Lp(a) = lipoprotein(a); TEAE = treatment-emergent adverse event; VLDL-C = very low-density lipoprotein.

^a In-house residency from Day -1 through the completion of all assessments on Day 4.

^b Physical examination to include neurologic examination.

^c Interim medical history only.

^d ECG will be single trace (1 x 10-second tracing), prior to safety blood draws or invasive procedures.

^e Sitting blood pressure, sitting pulse rate, respiratory rate and temperature. Pulse rate and BP will be measured using the same arm for each reading after the subject has been resting in the sitting position for at least 5 minutes.

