8.6.2. Clinical Laboratory Parameters

All clinical laboratory parameters will be listed; any value outside the clinical reference range will be flagged. Separate listings will be provided for any parameter for which there is any individual subject value outside the respective clinical reference range.

Summary tables by timepoint along with change from baseline and percent change from baseline will be provided for clinical chemistry and hematology parameters based on safety analysis set. The baseline is defined as the last reading before dosing.

Values recorded as $<x$, $\leq x$, $>x$, or $\geq x$ will be displayed in the listings as recorded. For the derivation of listing flags and calculation of summary statistics, $<x$ and $\leq x$ values will be set to BLQ, whereas $>x$ and $\geq x$ values will be set to x.

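### The SAP's exclusion of additional predose laboratory and lipid values conflicts with its own baseline definitions, so a triglyceride value rejected on retest (and possibly a Check-in ALT/AST value) could enter baseline.

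*SAP*

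**What the plan says.** SAP 8.1.2 has two rules for extra readings. For vital signs and ECG, an additional predose reading is a repeat, and the last repeat replaces the original in every calculation. Everything else is handled differently: "For all other data types (eg, laboratory parameters), any value recorded in addition to the original value will be defined as an unscheduled value". Then: "As unscheduled values are not associated with any scheduled timepoint, they will be excluded from all calculations". SAP 8.1 gives the scope of that phrase: "Where reference is made to 'all calculations', this includes, but is not limited to, summary statistics, statistical analyses and any parameter derivations". Baseline is a derived quantity, so on its face the exclusion reaches it.

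The baseline definitions carry no such restriction. For clinical laboratory data, SAP 8.6.2 says: "The baseline is defined as the last reading before dosing". For PD data, SAP 8.5.4 averages the two most recent non-missing values taken before the dose, or uses the single value if only one exists. Neither is limited to scheduled readings.

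Protocol 7.1.1 provides for retests: "Laboratory assessments used to determine subject eligibility may be repeated once for confirmation". After a retest, "the value that is closest to the enrollment date will apply for the determination of eligibility". Exclusion 15 sets a triglyceride limit at Screening. Exclusion 9 sets ALT/AST limits at Screening or Check-in.

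**The concern.** For a predose retest, two programmers could each follow the SAP and derive different baselines. The choice is not neutral. A triglyceride or ALT/AST test that is repeated to establish eligibility, and leads to enrollment, had a first result above the limit and a second within it. If the first result stays in baseline, the subject starts too high and every later change is shifted downward. For triglycerides this looks like a lipid reduction, and lipids are a secondary endpoint. For ALT/AST it understates a rise, and liver enzyme elevation is one of the two important potential risks named in protocol 1.5.2. Vital signs and ECG avoid the problem because the repeat replaces the original.

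**Working it through.** The plan gives no figure on this point to reproduce. The check applies the rules to the scheduled draws and then sizes the effect on assumed values.

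**Scheduled predose draws (protocol Appendix 9, checked against the sample counts in Appendix 3)**

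- Lipid panel: Screening (triglycerides only) and Day 1 predose, then 5 postdose draws. 2 + 5 = 7, matching the 7 samples in Appendix 3.
- The row "Chemistry & Hematology": Screening and Check-in (Day -1), then 2 in-house postdose draws and 8 from Day 7 onward. 1 + 1 + 2 + 8 = 12, matching Appendix 3.

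The counts leave no further scheduled predose draw for either.

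**Case (a): Screening triglycerides are repeated.** The retest falls within the 7.1.1 allowance. Let T0 be the original, T1 the retest and T2 the Day 1 predose value.

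- If 8.1.2 prevails: baseline = (T0 + T2)/2.
- If 8.5.4 is read literally: baseline = (T1 + T2)/2.
- Difference = (T0 - T1)/2.

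Assumed values in mmol/L: T0 = 6.0 (above the 5.65 limit), T1 = 4.0, T2 = 4.0, postdose 4.0.

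- 8.1.2: baseline (6.0 + 4.0)/2 = 5.0; change 4.0 - 5.0 = -1.0, or -20%.
- 8.5.4: baseline (4.0 + 4.0)/2 = 4.0; change 0, or 0%.
- Shift in a group mean from one such subject: 1.0/12 = 0.083 mmol/L with 12 subjects, 1.0/8 = 0.125 with 8. In mean percent change: 20/12 = 1.7 and 20/8 = 2.5 percentage points.

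The shift approaches zero when T0 and T1 lie just either side of 5.65, and grows by half of any wider gap.

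**Case (b): chemistry, such as ALT/AST.**

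- Retest at Screening: the scheduled Check-in result comes later and is the baseline under either rule. The rejected Screening value could be baseline only if Check-in were missing.
- Retest of the Check-in sample before dosing: 8.1.2 gives the rejected Check-in value; 8.6.2 read literally gives the retest.

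Whether the second situation can arise is unclear. Protocol 7.1.1 ties the repeat to the 40-day screening period. Appendix 9 labels Screening Day -40 to -2 and puts Check-in in its own column. Protocol 4.1 counts 40 days back from Day 1, which takes in Day -1. Exclusion 9 applies at Check-in and does not mention repeats.

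Assumed values in multiples of ULN: original 1.2, retest 0.8, postdose 2.0.

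- Original as baseline: 2.0 - 1.2 = +0.8, or 0.8/1.2 = +67%.
- Retest as baseline: 2.0 - 0.8 = +1.2, or 1.2/0.8 = +150%.

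Over assumed originals of 1.11 to 1.5 and retests of 0.6 to 1.1:

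| | Smallest | Largest |
|---|---|---|
| Understatement for the subject (x ULN) | 1.11 - 1.1 = 0.01 | 1.5 - 0.6 = 0.90 |
| Shift in a mean of 12 | 0.01/12 = 0.001 | 0.90/12 = 0.075 |
| Shift in a mean of 8 (33.3% drop-out) | 0.01/8 = 0.001 | 0.90/8 = 0.113 |

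**The case against.** The strongest reply is that there is no real conflict. Section 8.6.2 is the specific rule and could be taken to override the general one. The reason 8.1.2 gives, that these values have no scheduled timepoint, fits by-timepoint summaries better than a baseline defined by order before dosing. On that reading the retest counts and no bias arises. This is reasonable, but the SAP does not say it, and 8.1 expressly extends the exclusion to derivations.

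A reader might infer that any subject enrolled on a retest is given the rejected value as baseline. The documents do not support this. For chemistry, the Check-in draw supersedes a Screening retest under either rule, and a Check-in retest is not clearly permitted.

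A reader might also infer that a liver-enzyme rise could be hidden. That goes too far. Summaries of the values by timepoint do not use baseline. All laboratory values are listed, with out-of-range results flagged and separately listed. The > 3 x ULN trigger in protocol Appendix 7, for subjects with normal hepatic function at Screening, does not use the SAP baseline. No inferential analysis is planned.

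Two further objections stand. The documents give no retest frequency, so the number of affected subjects may be zero. Admitting retests also has a cost: a retest that had to pass an entry limit is itself mildly selected to be low, which pushes later change slightly upward.

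**Conclusion.** The conflict is real, and the SAP does not resolve it. If 8.1.2 prevails, change from baseline is biased downward for subjects whose Screening triglycerides were repeated and, if Check-in repeats are allowed, for those whose Check-in chemistry was repeated. In the assumed triglyceride example the subject shows -20% instead of 0%. For ALT, one retested subject moves a 12-subject mean by about 0.001 to 0.075 x ULN on the assumed ranges. All these magnitudes rest on assumed values, because the documents contain no triglyceride or ALT data. The effect is small, descriptive and confined to change and percent-change summaries, so this is a minor point that is worth correcting because the correction is simple.

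**What to change.** In the SAP:

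- 8.1.2: state that the exclusion of unscheduled values does not apply to the derivation of baseline.
- 8.6.2: define laboratory baseline as the last non-missing predose value, scheduled or unscheduled.
- 8.5.4: state that a retest replaces the value it repeats before the last two predose values are averaged. This also prevents an original and its own retest from being averaged together when the Day 1 predose value is missing.

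In the protocol, reconcile 4.1, 7.1.1, exclusion 9 and Appendix 9 on whether Check-in laboratory tests may be repeated. If the SAP can no longer be amended, the study report should state which rule was applied and to how many subjects.

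The cost is a few sentences and a small change to the baseline derivation, with no new data. The mild selection of retests noted above remains and can be acknowledged in the report.
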